anti-HCV	hepatitis C virus antibody
AST	aspartate transaminase
BfArM	The Federal Institute for Drugs and Medical Devices (Germany)
CAD	cold agglutinin disease
CFR	Code of Federal Regulations
CKD-EPI	Chronic Kidney Disease Epidemiology Collaboration Equation
СМН	Cochran-Mantel-Haenszel
CMV	cytomegalovirus
COVID-19	coronavirus disease 2019
CSR	Clinical Study Report
CTCAE	Common Terminology Criteria for Adverse Events
CYP	cytochrome P450
DAT	direct antiglobulin test
DNA	deoxyribonucleic acid
DSMB	Data Safety Monitoring Board
ECG	electrocardiogram
ECI	Events of Clinical Interest
eCRF	electronic case report form
EDC	electronic data capture
eDSMB	external Data Safety Monitoring Board
eGFR	estimated glomerular filtration rate
EOS	end of study
ЕОТ	end of treatment
EQ-VAS	EuroQol Visual Analogue Scale
FACIT	Functional Assessment of Chronic Illness Therapy

Abbreviations and Special Terms	Definition
FACIT-F	Functional Assessment of Chronic Illness Therapy – Fatigue
Fc	fragment crystallizable
FDA	Food and Drug Administration (US)
FSH	follicle-stimulating hormone
FUP	follow-up period
GCP	Good Clinical Practice
GDPR	General Data Protection Regulation
HBV	hepatitis B virus
HCV	hepatitis C virus
Hemoglobin response	A hemoglobin level ≥ 10 g/dL with a 2 g/dL increase from baseline (Day 1)
HIPAA	Health Insurance Portability and Accountability Act of 1996
HRT	hormonal replacement therapy
IB	Investigator's Brochure
IC ₅₀	concentration that results in 50% inhibition
IC ₉₀	concentration that results in 90% inhibition
ICF	informed consent form
ICH	International Council for Harmonisation of Technical Requirements for Pharmaceuticals for Human Use
IEC	independent ethics committee
IFN-γ	interferon γ
IgG	immunoglobulin G
IgM	immunoglobulin M
IL	interleukin
IQRMP	Integrated Quality Risk Management Plan
IRB	institutional review board
IRT	interactive response technology
ITT	intent to treat
IVIG	intravenous immunoglobulin
MedDRA	Medical Dictionary for Regulatory Activities
MHRA	Medicines & Healthcare products Regulatory Agency
NCCN	National Comprehensive Cancer Network
PBMC	peripheral blood mononuclear cell
PHL	potential Hy's law

Abbreviations and Special Terms	Definition
PI3K	phosphoinositide 3-kinase
РЈР	Pneumocystis jirovecii pneumonia
PMDA	Pharmaceuticals and Medical Devices Agency
PP	per protocol
PRO	patient-reported outcome
QD	once daily
RBC	red blood cell
RNA	ribonucleic acid
RSI	Reference Safety Information
SAE	serious adverse event
SoA	schedule of activities
SOP	standard operating procedure
Study drug	Parsaclisib or matching placebo
TEAE	treatment-emergent adverse event
ULN	upper limit of normal
wAIHA	warm autoimmune hemolytic anemia
WBC	white blood cell
WOCBP	woman of childbearing potential

1. PROTOCOL SUMMARY

Protocol Title:

A Phase 3, Randomized, Double-Blind, Placebo-Controlled Study of the Efficacy and Safety of Parsaclisib in Participants With Primary Warm Autoimmune Hemolytic Anemia (PATHWAY)

Protocol Number: INCB 50465-309

Objectives and Endpoints:

Table 1 presents the primary and major/key secondary objectives and endpoints.

Table 1: Primary and Secondary Objectives and Endpoints

Objectives	Endpoints	
Primary		
To evaluate the efficacy of parsaclisib in the treatment of participants with wAIHA.	 Proportion of participants attaining a durable hemoglobin response, defined as hemoglobin ≥ 10 g/dL with an increase from baseline of ≥ 2 g/dL not attributed to rescue therapy at ≥ 3 of the 4 available visits at Week 12 and/or later during the 24-week double-blind treatment period. 	
Key Secondary		
To further evaluate the efficacy of parsaclisib in the treatment of participants with wAIHA.	 Proportion of participants with a ≥ 3-point increase from baseline in FACIT-F score at Week 24. 	

Overall Design:

Table 2 presents the key study design elements. Further study details are presented after the table.

[figure not shown]
Table 2: Key Study Design Elements

Study Phase	Phase 3
Clinical Indication	Primary wAIHA
Population	Men and women, aged 18 years or older with primary wAIHA, a hemoglobin level ≥ 6.5 to < 10 g/dL with symptomatic anemia at screening, a FACIT-F score ≤ 43 at screening without an underlying lymphoproliferative malignancy or AIHA secondary to an autoimmune-related condition who have failed at least 1 prior standard therapy that is known to confer clinical benefit or who are intolerant to treatment or for whom treatment is contraindicated.
Number of Participants	Approximately 100 participants will be randomized 2:1 (approximately 67:33) to receive either parsaclisib or matched placebo. Participants will be stratified by hemoglobin at screening as determined by local laboratory (hemoglobin $< 9 \text{ g/dL or} \ge 9 \text{ g/dL}$), and corticosteroid (prednisone or equivalent) dose at screening ($\le 20 \text{ mg/day vs} > 20 \text{ mg/day}$). Note: Japan must meet a minimum enrollment regulatory requirement; therefore, enrollment in Japan may continue after enrollment in other countries
	ends. Note: Upon implementation of Protocol Amendment 2, the study will be closed to further enrollment due to the change in the regulatory landscape for PI3K inhibitors and the challenges and subsequent low numbers in enrollment.
Study Design	Randomized, double-blind, placebo-controlled, multicenter study
Estimated Duration of Study Participation	Screening period: Up to 32 days. Double-blind treatment period: 24 weeks. Open-label treatment period: 24 weeks. Long-term extension: approximately 2 years Post-treatment follow-up visits: 12 weeks. It is estimated that an individual will participate for approximately 3 years. Note: Upon implementation of Protocol Amendment 2, protocol-required procedures and visits will be reduced or eliminated for ongoing participants.
DSMB	Yes (external)
Coordinating Principal Investigators	Prof. , Austria Dr. , Italy

Treatment Groups and Duration:

The study design is shown in Figure 1. The SoA for the double-blind treatment period, open-label treatment period, and long-term extension are detailed in Table 3, Table 4, and Table 5, respectively. The specific laboratory analytes are described in Table 11.

Figure 1: Study Design Schema

^a Hemoglobin at screening as determined by local laboratory (< 9 g/dL or \geq 9 g/dL) and corticosteroid (prednisone or equivalent) dose at screening (\leq 20 mg/day vs > 20 mg/day)

Participants will receive parsaclisib 2.5 mg QD or matching placebo QD for 24 weeks during the double-blind treatment period. All participants who complete the double-blind treatment period, are tolerating study treatment, and in the investigator's opinion may benefit from treatment may continue into an open-label treatment period for an additional 24 weeks of parsaclisib QD. All participants who complete the open-label treatment period, are tolerating study treatment, and in the investigator's opinion may benefit from continued treatment may enter into the long-term extension. During the long-term extension, participants may take a drug holiday 1 time with the option for re-treatment if they experience worsening of wAIHA after the drug holiday.

Note: Upon implementation of Protocol Amendment 2:

- Participants randomized to placebo during the 24-week double-blind treatment period may receive parsaclisib before reaching Week 24.
- Once treatment with parsaclisib is started, participants will enter the open-label treatment period (see Table 4) regardless of visits completed during the double-blind treatment period.

Participants who permanently discontinue study treatment will enter the 12-week post-treatment follow-up period, which includes 3 visits (1 every 4 weeks) to assess safety and persistence of effect.

Note: Upon implementation of Protocol Amendment 2:

- Participants receiving parsaclisib who permanently discontinue study drug will enter the post-treatment follow-up period for 1 visit (FUP1/EOS) approximately 4 weeks after the last dose of study drug.
- Participants receiving placebo who permanently discontinue study drug will no longer be required to enter the post-treatment follow-up period and will perform EOT/EOS upon discontinuation of treatment.

^b The primary analysis will be conducted when the last randomized participant has completed the 24-week, double-blind treatment period.

Throughout the study, dose reductions from 2.5 mg to 1 mg are allowed due to intolerable AEs or hemoglobin levels in the high end of normal range that in the investigator's opinion requires a dose reduction. During the study, the investigator may treat a participant with low hemoglobin or symptomatic anemia requiring treatment according to the rescue treatment plan (Section 6.7.4).

Adherence to the study design requirements, including those specified in the SoA, is essential and required for study conduct.

Note: Upon implementation of Protocol Amendment 2, protocol-required procedures and visits will be reduced or eliminated for ongoing participants (see Table 3, Table 4, and respective sections for details).

Table 3: Schedule of Activities (Double-Blind)

	Screening Double-Blind Treatment Period											
	Day -32		W2	W4	W6	W8	W10	W12	W16	W20	EOT1a/EOSb	
Visit Day (Range)	to -1	Day 1			$\pm 3 d$				± 3 d		$W24 \pm 3 d$	Notes and Protocol Section
In-office visit	X	X	X	X		X		X	X	X	X	
Remote visit					X		X					May be performed in office at the discretion of the investigator. Note: Where local laws and/or regulations do not permit remote visits, these assessments will be performed in office.
Administrative procedures												
Informed consent	X											Section 8.1.1
Contact IRT	X	X	X	X		X		X	X	X	X	Section 8.1.3
Inclusion/exclusion criteria	X	X										Section 5.1 and Section 5.2
Demography, wAIHA disease history and medical history and AIHA symptoms	X											Demography will be collected as permitted per local regulations. Section 8.1.5
Prior/concomitant medications	X	X	X	X	X	X	X	X	X	X	X	Section 6.7
Randomize to treatment arm		X										Section 6.3 and Section 8.1.3
Distribute reminder cards		X	X	X		X		X	X	X	X	Section 8.1.4
Dispense study drug		X	X	X		X		X	X	X	X*	*Participants continuing into open-label treatment period. Section 6.1 and Section 8.1.3
Study drug return, accountability and compliance assessment			X	X		X		X	X	X	X	Section 6.4
Prophylactic treatment for PJP				As pres	scribed	by the i	nvestig	ator the	oughou	ıt study		Section 6.7.1.1
Healthcare resource utilization*		X	X	X		X		X	X	X	X	Section 8.3.8
												*No longer required upon implementation of Protocol Amendment 2.
Safety assessments												
Comprehensive physical examination	X										X	Height and weight at screening only. Section 8.4.2
Targeted physical examination		X		X		X		X	X	X		Section 8.4.2

Table 3: Schedule of Activities (Double-Blind) (Continued)

	Screening				Doub	le-Blin	d Trea	tment	Period			
	Day -32		W2	W4	W6	W8	W10	W12	W16	W20	EOT1a/EOSb	
Visit Day (Range)	to -1	Day 1	$\pm 3 d$	± 3 d	$\mathbf{W24} \pm 3 \ \mathbf{d}$	Notes and Protocol Section						
Safety assessments (continued)												
Vital signs	X	X	X	X	X	X	X	X	X	X	X	Section 8.4.3
12-lead ECG	X							X			X	Section 8.4.4
AE assessment	X	X	X	X	X	X	X	X	X	X	X	Section 9
Laboratory assessments ^c						•				•		
Serum FSH	X											Confirmation of lack of childbearing potential.
Serology	X						X*					Hepatitis tests should be performed early in the screening process due to the length of time needed to obtain the results. *CMV testing only and monitor as clinically indicated Section 8.4.5.2
D-dimer	X			X		X		X		X	X	Section 8.4.5
Vitamin B12/folic acid	X											Section 8.4.5
Serum pregnancy	X										X	WOCBP only. Section 8.4.5.1
Urine pregnancy		X		X		X		X	X	X		WOCBP only. Section 8.4.5.1
Urinalysis	X											Section 8.4.5
Serum chemistry	X	X		X		X		X	X	X	X	Section 8.4.5
Efficacy assessments	•	•										
Hematology	X	X	X*	X	X*	X	X*	X	X	X	X	Section 8.2.1 and Section 8.4.5 *No longer required upon implementation of Protocol Amendment 2.
DAT	X										X	Section 8.2.1 and Section 8.4.5

Table 3: Schedule of Activities (Double-Blind) (Continued)

	Screening				Doub	le-Bline	d Treat	ment P	Period			
	Day -32		W2	W4	W6	W8	W10	W12	W16	W20	EOT1a/EOSb	
Visit Day (Range)	to -1	Day 1	$\pm 3 d$	$W24 \pm 3 d$	Notes and Protocol Section							
PRO and clinical outcome assess	sments (Not	te: Upoi	ı imple	mentat	ion of l	Protoco	ol Ame	ndmen	t 2, the	PROs	noted herein w	ill no longer be required)
FACIT-F scale	X	X				X		X	X	X	X	Should be completed before any other assessments. Must be completed before all other PRO assessments. Section 8.3.1
6MWT		X									X	Vital signs should be conducted pre- and post-test. 6MWT must be performed after all other PRO assessments are completed. Section 8.3.2

Table 3: Schedule of Activities (Double-Blind) (Continued)

	Screening		Double-Blind Treatment Period									
	Day -32		W2	W4	W6	W8	W10	W12	W16	W20	EOT1a/EOSb	
Visit Day (Range)	to -1	Day 1	$\pm 3 d$	$\pm 3 d$	$\pm 3 d$	$\pm 3 d$	$\pm 3 d$	$\pm 3 d$	$\pm 3 d$	$\pm 3 d$	$W24 \pm 3 d$	Notes and Protocol Section

^a Participants receiving parsaclisib who permanently discontinue study drug will enter the post-treatment follow-up period (see Table 4 and Section 8.10).

VV-CLIN-014098 CONFIDENTIAL

^b Participants receiving placebo who permanently discontinue study drug will no longer be required to enter the post-treatment follow-up period and will perform EOT1/EOS upon discontinuation of treatment.

^c Fasting is not required for central laboratory assessments.

 Table 4:
 Schedule of Activities (Open-Label)

		1	o	pen-Lab	el Treat	ment				st-Treatm Follow-U _l		
Visit Day (Range)	W26 ± 3 d	W28 ± 5 d	W30 ± 5 d	W32 ± 5 d	W36 ± 5 d	W40 ± 5 d	W44 ± 5 d	EOT2 W48 ± 5 d	FUP1a/ EOS	FUP2b	FUP3 ^b	Notes and Protocol Section
In-office visit		X		X	X	X	X	X	X		X	
Remote visit	X		X							X		May be performed in-office at the discretion of the investigator. Note: Where local laws and/or regulations do not permit remote visits, these assessments will be performed in office.
Administrative procedures												
Prior/concomitant medications	X	X	X	X	X	X	X	X	X	X	X	Section 6.7
Contact IRT		X		X	X	X	X	X	X		X	Section 8.1.3
Distribute reminder cards		X		X	X	X	X	X				Section 8.1.4
Dispense study drug		X		X	X	X	X	X*				*Participants continuing into long-term extension. Section 6.1 and Section 8.1.3
Study drug return, accountability and compliance assessment		X		X	X	X	X	X				Section 6.4
Prophylactic treatment for PJP				As presc	ribed by	the invest	igator thro	oughout st	udy			Section 6.7.1.1
Healthcare resource utilization*		X		X	X	X	X	X			X	*No longer required upon implementation of Protocol Amendment 2.
Safety assessments												
AE assessments	X	X	X	X	X	X	X	X	X	X	X	Section 8.4.1
Comprehensive physical examination						_		X	X		X	Section 8.4.2
Targeted physical examination		X		X	X	X	X					Section 8.4.2
Vital signs	X	X	X	X	X	X	X	X	X	X	X	Section 8.4.3
12-lead ECG								X				Section 8.4.4

Table 4: Schedule of Activities (Open-Label) (Continued)

			0	pen-Lab	el Treat	ment				st-Treatm Follow-Uj		
Visit Day (Range)	W26 ± 3 d	W28 ± 5 d	W30 ± 5 d	W32 ± 5 d	W36 ± 5 d	W40 ± 5 d	W44 ± 5 d	EOT2 W48 ± 5 d	FUP1a/ EOS	FUP2 ^b	FUP3 ^b	Notes and Protocol Section
Efficacy assessments	1	ı		1								
Hematology	X*	X	X*	X	X	X	X	X	X	X	X	*No longer required upon implementation of Protocol Amendment 2.
DAT								X				Section 8.2.1 and Section 8.4.5
PRO and clinical outcome asses	sments (Note: U	pon imp	olementa	tion of P	rotocol A	mendme	nt 2, the l	PROs note	d herein	will no lo	
FACIT-F scale		X		X		X		X			X	Should be completed before any other assessments. Must be completed before all other PRO assessments. Section 8.3.1

Table 4: Schedule of Activities (Open-Label) (Continued)

			0	pen-Lab	el Treat	ment				st-Treatm Follow-Uj		
	W26	W28	W30	W32	W36	W40	W44	EOT2 W48	FUP1a/	THE	ELIDAL	
Visit Day (Range) PRO and clinical outcome assess	±3 d	±5d	± 5 d	±5d	±5d	±5d	±5d	±5d	EOS	FUP2b	FUP3b	Notes and Protocol Section
6MWT	sments (continue	u) (Note	: Ороп	пприете	псистоп о	Protoco	X	ment 2, the	e PROS III	X	Vital signs should be conducted pre- and post-test. 6MWT must be performed after all other PRO assessments are completed. Section 8.3.2
Laboratory assessments ^c D-dimer		X		X	X		X	X				Section 8.4.5
Serum pregnancy								X			X	WOCBP only. Section 8.4.5.1
Urine pregnancy		X		X		X			X	X		WOCBP only. Section 8.4.5.1
Serum chemistry CMV		X		X	X X*	X	X	X	X	X	X	Section 8.4.5 *Monitor as clinically indicated

a Only required for participants receiving parsaclisib; post-treatment follow-up visit to be conducted 4 weeks (± 5 days) after EOT visit (or after the last dose of study drug if the EOT visit was not performed).

^b No longer required upon implementation of Protocol Amendment 2.

^c Fasting is not required for central laboratory assessments.

 Table 5:
 Schedule of Activities (Long-Term Extension)

		Long-Tern			
Visit Day (Range)	W56 (± 7 d)	Every 8 Weeks (± 7 d)	Every 16 Weeks (± 7 d)	EOT3a	Notes and Protocol Section
In-office visit	X	X		X	
Administrative procedures					·
Contact IRT	X	X		X	Section 8.1.3
Prior/concomitant medications	X	X		X	Section 6.7
Distribute reminder cards	X	X		X	Section 8.1.4
Dispense study drug	X	X			Section 6.1 and Section 8.1.3
Study drug return, accountability and compliance assessment	X	X		X	Section 6.4
Prophylactic treatment for PJP		As prescribed by the inve	estigator throughout study		Section 6.7.1.1
Healthcare resource utilization	X		X	X	Section 8.3.8
Safety assessments		-	1		
Comprehensive physical examination				X	Section 8.4.2
Targeted physical examination	X	X			Section 8.4.2
Vital signs	X	X		X	Section 8.4.3
AE assessment	X	X		X	Section 8.4.1
Laboratory assessments ^b					·
CMV		X	[*		*Monitor as clinically indicated
D-dimer		X	(*		*Perform as clinically indicated Section 8.4.5
Serum pregnancy				X	WOCBP only. Section 8.4.5.1
Urine pregnancy	X	X			WOCBP only. Section 8.4.5.1
Serum chemistry	X	X		X	Section 8.4.5
Efficacy assessments		.			
Hematology	X	X		X	Section 8.2.1 and Section 8.4.5
DAT				X	Section 8.2.1 and Section 8.4.5

Table 5: Schedule of Activities (Long-Term Extension) (Continued)

	W56	Every 8 Weeks	Every 16 Weeks		
Visit Day (Range)	$(\pm 7 d)$	$(\pm 7 d)$	(± 7 d)	EOT3 ^a	Notes and Protocol Section
PRO and clinical outcome assessments	nger be required				
FACIT-F scale	X		X	X	Should be completed before any other assessments.
					Must be completed before all other PRO
					assessments.
					Section 8.3.1

^a Participants receiving parsaclisib who permanently discontinue study drug will enter the post-treatment follow-up period (see Table 4 and Section 8.10).

^b Fasting is not required for central laboratory assessments.

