2.3. Benefit/Risk Assessment

Parsaclisib monotherapy provided a durable improvement in hemoglobin in participants with AIHA (see Section 2.2.2). The safety profile for parsaclisib is described in the parsaclisib IB. Briefly, AEs were observed in participants administered parsaclisib monotherapy in inflammatory and autoimmune indications (N = 35), with the most common (in \geq 10% of participants) being diarrhea and pyrexia (22.9% each); headache and rash (14.3% each); and AIHA, nausea, and peripheral edema (11.4% each). Parsaclisib has effects on the immune system and serious infection events have occurred in patients treated with parsaclisib, including PJP, CMV, and COVID-19. Due to the severity, these events may impact the benefit-risk balance of parsaclisib if not managed appropriately. Furthermore, a pharmacological effect of concurrent corticosteroid use or recent rituximab therapy can contribute to further immunosuppression and such effects pose an additional risk of infections. In an effort to manage this risk, guidelines for managing serious infections have been implemented in this study, and include careful monitoring and supportive care measures. If supportive care interventions are unsuccessful and causes other than parsaclisib-related infections have been ruled out, then either parsaclisib dose modification or permanent discontinuation is recommended. Participants are required to receive a standard PJP prophylaxis regimen while receiving parsaclisib as described in Section 6.7.1.1. Information regarding the additional risks of diarrhea or colitis, neutropenia, and severe cutaneous reactions is outlined in the Warnings and Precautions of the parsaclisib IB. Dose modification guidance and supportive care guidelines for these AEs have been implemented in this study, and participants will be closely monitored for evidence of toxicities, including long-term toxicities.

More detailed information about the known and expected benefits and risks and reasonably expected AEs of parsaclisib may be found in the parsaclisib IB.

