All participants who complete the 24-week double-blind treatment period, are tolerating study treatment, and in the investigator's opinion may benefit from treatment may enter the 24-week open-label treatment period and will receive parsaclisib administered at the same dose and schedule as in the double-blind treatment period.

Note: Upon implementation of Protocol Amendment 2:

- Participants randomized to placebo during the 24-week double-blind treatment period may receive parsaclisib before reaching Week 24.
- Once treatment with parsaclisib is started, participants will enter the open-label treatment period (see Table 4) regardless of visits completed during the double-blind treatment period.

All participants who complete the open-label treatment period, are tolerating study treatment, and in the investigator's opinion may benefit from continued treatment, may enter into the long-term extension. Parsaclisib will be administered at the same dose and schedule as in the open-label treatment period. During the long-term extension, participants may take a drug holiday 1 time with the option for re-treatment if they experience worsening of wAIHA after interrupting parsaclisib (see Section 6.6 for re-treatment criteria).

Participants will receive study treatment until any of the criteria for permanent discontinuation of study drug are met (see Section 7.1.1). Participants who permanently discontinue study treatment will enter the 12-week post-treatment follow-up period with visits scheduled every 4 weeks for 12 weeks after the last dose of study drug.

Note: Upon implementation of Protocol Amendment 2:

- Participants receiving parsaclisib who permanently discontinue study drug will enter the post-treatment follow-up period for 1 visit (FUP1/EOS) approximately 4 weeks after the last dose of study drug.
- Participants receiving placebo who permanently discontinue study drug will no longer be required to enter the post-treatment follow-up period and will perform EOT1/EOS upon discontinuation of treatment.

An external DSMB will review safety data periodically throughout the study as defined in the DSMB charter and may provide recommendations regarding changes in the study conduct (see Section 5.6).

Participants will be assessed for efficacy by monitoring hemoglobin level	
and completing the FACIT-F to assess self-reported fatigue and its impact upon daily activities	
and function.	
	ĺ
The primary analysis will be conducted when the last randomized	

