8.9. End of Treatment

When the participant permanently discontinues study drug, then the EOT visit (EOT1 for double-blind period, EOT2 for open-label period, and EOT3 for long-term extension) should be

conducted. If the EOT visit coincides with a regular study visit, the EOT evaluations will supersede those of that scheduled visit, and the data should be entered in the EOT visit in the eCRF. The participant should enter the post-treatment follow-up visits.

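### Amendment 2 sends early-crossover placebo participants to Table 4 without saying what its Weeks 26 to 48 are counted from or which visit precedes the first parsaclisib dose

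*Protocol*

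**What the plan says.** The Amendment 2 note in the protocol summary says: "Participants randomized to placebo during the 24-week double-blind treatment period may receive parsaclisib before reaching Week 24". It gives no earliest week. It then moves these people to the open-label schedule: "participants will enter the open-label treatment period (see Table 4) regardless of visits completed during the double-blind treatment period". Section 4.1 repeats both statements and adds no counting rule.

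Table 4 was laid out to follow a completed Week 24 visit. Its treatment columns run from W26 to W48.
- W26 is remote. It keeps adverse events, vital signs and concomitant medications, but its hematology (like that at W30) is marked "No longer required upon implementation of Protocol Amendment 2".
- The first chemistry, the first retained hematology, the first D-dimer and the first dispensing are at W28.

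Dispensing for open-label entry sits in the Table 3 EOT1/W24 column, footnoted "Participants continuing into open-label treatment period". That column also carries a comprehensive physical examination, ECG, chemistry, hematology, D-dimer and a serum pregnancy test. Before Week 24, EOT1 is triggered differently. Section 8.9 begins "When the participant permanently discontinues study drug, then the EOT visit", and Section 7.1.2 agrees. Study drug is defined to cover both parsaclisib and placebo, so a switch from one to the other is not clearly a discontinuation.

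Table 2 gives the planned length: "Open-label treatment period: 24 weeks". The protocol summary also makes adherence to the schedules of activities mandatory.

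**The concern.** Early-crossover participants are taking parsaclisib for the first time. Section 2.3 promises that "participants will be closely monitored for evidence of toxicities, including long-term toxicities", and the interruption steps in Table 9 depend on ALT, AST, neutrophil and platelet results. If two sites can follow the same schedule and obtain the first on-drug laboratory results at 4 weeks or at 24 weeks, the protocol does not reliably deliver that monitoring.

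The ambiguity carries into the analysis. The SAP summarizes laboratory values by visit (Section 9.3.1) and takes baseline before the first study drug (Section 4.1.3), which for these people is placebo. Its separate placebo-to-parsaclisib group applies to exposure, compliance and adverse events only (Section 5.2). Laboratory values, vital signs and ECGs taken after crossover therefore default to the Day 1 placebo group, under week labels with no defined meaning.

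**Working it through.** **Inputs**
- x = study week of first parsaclisib, x < 24 (Amendment 2 note).
- Table 4: first contact W26; first chemistry, retained hematology and dispensing W28 (± 5 days); last treatment visit W48.
- Stated open-label length: 24 weeks (Table 2).
- Table 3 chemistry and retained hematology: Day 1 and Weeks 4, 8, 12, 16, 20 and 24.

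**Step 1. Reproduce the plan's own figure.** For crossover at Week 24 as first designed, open-label length is 48 − 24 = 24 weeks, as stated. First contact is at 26 − 24 = 2 weeks and first laboratory tests at 28 − 24 = 4 weeks.

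**Step 2. Read Table 4 as study weeks from Day 1.**

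| Crossover week x | First contact, 26 − x | First labs and dispensing, 28 − x | Open-label length, 48 − x |
|---|---|---|---|
| 4 | 22 | 24 | 44 |
| 8 | 18 | 20 | 40 |
| 12 | 14 | 16 | 36 |
| 16 | 10 | 12 | 32 |
| 20 | 6 | 8 | 28 |

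Every row contradicts the 24-week period. In the first row, Table 4 has no scheduled drug supply for 24 weeks. For comparison, a participant starting parsaclisib on Day 1 has laboratory tests at Week 4.

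**Step 3. Read Table 4 as counted from first parsaclisib**, so that its notional W24 is that dose. First contact is at 2 weeks, first laboratory tests at 4, then every 4 weeks, and open-label length is 24 weeks for any x.

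**Step 4. How small could x be?** The SAP dates the termination decision 17 April 2023, with 13 participants randomized and dosed. Amendment 2 is dated 10 May 2023, which is 23 days or 23/7 = 3.3 weeks later. Assume that nobody was randomized after the decision and nobody crossed over before the amendment date. Then x is at least 3.3, and the longest gap under Step 2 is 28 − 3.3 = 24.7 weeks.

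**Step 5. Results in hand before the first dose.** Until crossover, Table 3 schedules chemistry and hematology every 4 weeks. The last scheduled set is therefore normally no more than 4 weeks old, on either reading.

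**Step 6. How many people?** The placebo share is assumed to lie between one third (2:1) and one half (1:1, before Amendment 1). Of 13, that is 13/3 = 4.3 to 13/2 = 6.5, or about 4 to 7 on placebo. How many were still before Week 24 is not given, and it could be none.

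**The case against.** The best reply is that the study-week reading is hardly workable. It breaks the 24-week period and leaves a gap in drug supply. The note reads more naturally as leaving Table 3 and starting Table 4 at once than as waiting for Week 26. EOT1 is the only scheduled dispensing point for open-label entry and carries a full safety panel, so it can be read as the transition visit. Table 11 also calls for monthly pregnancy testing in women of childbearing potential and hematology to site standard of care, and Section 8.7 allows unscheduled visits. SAP Section 9.1 already makes the first-dose date treatment-specific for crossovers.

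Most of this stands, and it rules out three stronger readings that a reader might infer:
- **That Table 4 is fixed at study weeks and first exposure goes without safety laboratory tests for about 24 weeks.** That is one reading, and the less coherent one. It also passes over the testing in Table 11.
- **That there is no pre-dose check.** The documents support only that none is explicitly required for an early crossover.
- **That the ECG timing is an Amendment 2 defect.** If EOT1 precedes the first dose, the next ECG at W48 is what every placebo participant crossing at Week 24 would have had.

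The reply does not supply the missing sentence. No text states the anchor. EOT1 is not triggered by a switch, and moving people whatever visits they have completed leaves it open whether EOT1 must come first. None of the other provisions requires scheduled chemistry. A treatment-specific first-dose date does not define visit labels, and neither Section 4.1.3 nor Section 9.3.1 of the SAP resets the laboratory baseline.

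**Conclusion.** The concern holds as a contradiction within the protocol that should be corrected. The Amendment 2 notes route early crossovers to a table whose week labels, read literally, conflict with the protocol's own open-label length and with its dispensing schedule. No transition visit is named.

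The size depends on the reading. The first Table 4 laboratory tests come 8 to 24 weeks after crossover at Weeks 20 to 4 if the columns are study weeks, and at 4 weeks if they count from first parsaclisib. The longer gaps need the study-week reading and an assumed crossover week. The documents do not show that any participant experienced them. The affected number is unknown within an assumed placebo arm of about 4 to 7.

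**What to change.** Reconcile the Amendment 2 notes (protocol summary and Section 4.1), the Table 3 EOT1 column, Table 4 and Sections 7.1.2 and 8.9. They should state one anchor for the Table 4 weeks and name the visit that serves the transition to first parsaclisib. Which assessments that visit contains, and when ECGs or other monitoring fall, is for the sponsor to settle; none is proposed here.

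In the SAP, label post-crossover safety visits by weeks since first parsaclisib dose. Define a matching baseline, and extend the placebo-to-parsaclisib group to laboratory values, vital signs and ECGs. These summaries then have a defined meaning whichever way sites read Table 4.

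The cost is a footnote, a site letter and a small amount of SAP programming. The SAP is dated 17 January 2024, which is 252 days or 252/7 = 36 weeks after Amendment 2. If nobody was randomized after the amendment date, every double-blind period would have ended by then. At that point the SAP wording is the part that can still change what is reported.
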